## Stryker Neurovascular

**Document Title:** Trevo® Retriever Registry (China) Statistical Analysis Plan

**Document Number:** CDM10001420

**Ver AA**

4. Rate of study device and procedure related serious adverse events (SAE) through Day 90.

### 5.3. Additional Safety Analyses

#### Adverse Events

- All SAEs through Day 90.

All SAEs through Day 90 will be summarized by number of events, number of subjects with events and the percentages of subjects with events by the type of SAEs and by their relatedness.

- All AEs during procedure.

All AEs during procedure will be summarized by number of events, number of subjects with events and the percentages of the subjects with events by the type of AEs and by their relatedness.

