### 8.4 24 hours (-6/+24) post procedure

The following data will be collected at 24 hours (-6/+24) post procedure:

- NIHSS (see **appendix G**)
- SAEs related to the device or procedure.

**STRYKER CONFIDENTIAL** - THIS DOCUMENT CONTAINS CONFIDENTIAL AND PROPRIETARY INFORMATION THAT IS THE PROPERTY OF STRYKER CORPORATION. NEITHER THIS DOCUMENT NOR THE INFORMATION HEREIN MAY BE REPRODUCED, USED, OR DISCLOSED TO ANY THIRD PARTY WITHOUT THE PRIOR WRITTEN CONSENT OF STRYKER CORPORATION.

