## Trevo® Retriever Registry (China)

- For all subjects who expire prior to the 24 hours (-6/+24) assessment, available information regarding the primary cause of death and date/time of death will be recorded, as well as, whether the subject was made “do not resuscitate” (DNR) or “comfort care only” prior to expiration.

Any death or SAE must be reported to Stryker Neurovascular within 24 hours of becoming aware of the event(s).

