## 14 Adverse Events

The following adverse events will be reported:

- all adverse events that occur during the procedure
- all SAEs related to the device or the procedure through Day 90
- all serious adverse events that result in death through Day 90

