# Trevo® Retriever Registry (China)

## Appendix D. Time and Events Schedule

Time and Events Schedule						
Assessments:	Pre-procedure (Screening /Baseline)	Procedure	24 (-6/+24) hrs post procedure	Discharge (or Day 5-7 whichever comes first)	Day 30 +14 days	Day 90*** ±14 days
Inclusion/Exclusion Criteria	✓					
Informed Consent*	✓					
Demographics and Medical History	✓					
Baseline Medications	✓					
Baseline Labs (PT, PTT platelets, INR, glucose). Pregnancy test, if applicable	✓					
mRS**	✓			✓	✓	✓
NIHSS assessment	✓		✓	✓		
Stroke onset/etiology	✓			✓		
CT/MR Y	✓		✓			
Angiogram Procedure Information ****Y		✓				
Hospital Stay/Discharge Disposition				✓		
Post Discharge Follow-up****					✓	✓
Adverse Events †		✓	✓	✓	✓	✓
Utilization/Economic measures ††				✓		✓
Study Completion						✓

\*Written IC must be obtained prior to any data entry.  
 \*\*Telephone mRS assessment is acceptable if subject not able to return to the clinic in person.  
 \*\*\*\*Study Staff should review the study requirements with the subject and arrange all follow-up visits at discharge.  
† All AE during procedure and only DR and PR SAE, death post procedure.  
†† De-identify forms and enter subject ID # prior to sending to Stryker  
Y CT/MR and Angiographic images will be de-identified with subject ID# if submitted to SNV or the core lab.

**STRYKER CONFIDENTIAL - THIS DOCUMENT CONTAINS CONFIDENTIAL AND PROPRIETARY INFORMATION THAT IS THE PROPERTY OF STRYKER CORPORATION. NEITHER THIS DOCUMENT NOR THE INFORMATION HEREIN MAY BE REPRODUCED, USED, OR DISCLOSED TO ANY THIRD PARTY WITHOUT THE PRIOR WRITTEN CONSENT OF STRYKER CORPORATION.**

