**Ver AA**

**Table 12: All SAEs**

	# of events	Percentages of subjects with events* (Total subjects=xxx)
All SAEs		
Details of all SAEs	xx	xx.x% (xx/xxx)
...	xx	
...	xx	xx.x% (xx/xxx)
...	xx	xx.x% (xx/xxx)
Study device and procedure related SAEs		
Total	xx	xx.x% (xx/xxx)
Details of study device and procedure related SAEs	xx	xx.x% (xx/xxx)
...	xx	xx.x% (xx/xxx)
...	xx	xx.x% (xx/xxx)
...	xx	xx.x% (xx/xxx)
Study device related SAEs only		
Total	xx	xx.x% (xx/xxx)
Details of study device related SAEs	xx	xx.x% (xx/xxx)
...	xx	xx.x% (xx/xxx)
...	xx	xx.x% (xx/xxx)
...	xx	xx.x% (xx/xxx)
Procedure but not study device related SAEs		
Total	xx	xx.x% (xx/xxx)
Details of procedure but not study device related SAEs	xx	xx.x% (xx/xxx)
...	xx	xx.x% (xx/xxx)
...	xx	xx.x% (xx/xxx)
...	xx	xx.x% (xx/xxx)
Study device or procedure related SAEs		
Total	xx	xx.x% (xx/xxx)
Details of study device or procedure related SAEs	xx	xx.x% (xx/xxx)
...	xx	xx.x% (xx/xxx)
...	xx	xx.x% (xx/xxx)
Not study device and not procedure related SAEs		
Total	xx	xx.x% (xx/xxx)
Details of not study device and not procedure related SAEs	xx	xx.x% (xx/xxx)
...	xx	xx.x% (xx/xxx)
...	xx	xx.x% (xx/xxx)

\*: Some subjects may experience multiple events

STRYKER CONFIDENTIAL - THIS DOCUMENT CONTAINS CONFIDENTIAL AND PROPRIETARY INFORMATION THAT IS THE PROPERTY OF STRYKER CORPORATION. NEITHER THIS DOCUMENT NOR THE INFORMATION HEREIN MAY BE REPRODUCED, USED, OR DISCLOSED TO ANY THIRD PARTY WITHOUT THE PRIOR WRITTEN CONSENT OF STRYKER CORPORATION

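### SAP Table 12 reports all SAEs and unrelated SAEs through Day 90, but the protocol's post-procedure data items cover only related SAEs and deaths, so these two blocks may be incomplete

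*SAP*

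**What the plan says.** **SAP.** Section 5.3 plans that "All SAEs through Day 90 will be summarized by number of events, number of subjects with events and the percentages of subjects with events", split by type and relatedness. The Table 12 shell has six blocks, each with event counts and percentages of total subjects. The first is all SAEs; the last is "Not study device and not procedure related SAEs". Its only footnote says that a subject may have several events.

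**Protocol, data items.**
- Section 14 lists three reportable sets: "all adverse events that occur during the procedure", "all SAEs related to the device or the procedure through Day 90" and "all serious adverse events that result in death through Day 90".
- The footnote to Appendix D gives the same scope: "All AE during procedure and only DR and PR SAE, death post procedure".
- The visit lists in 8.4, 8.5, 8.6.1 and 8.6.2 ask for "SAEs related to the device or procedure", plus information on deaths.
- Section 14.3 sends to the eCRF the required AEs, which it explains as AEs resulting in death and device- and procedure-related AEs, serious or not.

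**Protocol, reporting to the sponsor.** Section 8.4 also says: "Any death or SAE must be reported to Stryker Neurovascular within 24 hours of becoming aware of the event(s". Sections 8.5, 8.6.1 and 8.6.2 repeat this almost word for word, with no limit by relatedness. Section 14.3 applies the same 24-hour duty only to required SAEs and to UADEs.

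**Protocol, relatedness.** Section 14.2 allows three answers for the device and three for the procedure: related, unrelated, unknown.

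**The concern.** The SAP promises totals that the protocol's own collection rules do not clearly supply. A non-fatal SAE after the procedure that is judged unrelated to both device and procedure appears in none of the data lists, yet it belongs in two Table 12 blocks by their labels. If the table is reported as labelled, a reader cannot tell whether such an event did not happen or was not collected.

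This matters because protocol 4.2 and SAP 2.1.2 say the registry data may support regulatory submissions and reimbursement dossiers, and name real-world safety data as an objective. An all-SAE percentage quoted from this registry could be read as a complete rate, or set beside one from a study that did collect every SAE.

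**Working it through.** The documents give no SAE rate for this registry, so there is no figure of the plan to reproduce. The check is a comparison of the rules, by type of SAE after the procedure.

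| SAE after the procedure | Section 14, Appendix D | Visit lists 8.4–8.6 | eCRF rule in 14.3 | Any-SAE sentences, read broadly | Table 12 blocks it belongs in |
|---|---|---|---|---|---|
| Judged related to device or procedure | yes | yes | yes | yes | first, and the related blocks |
| Fatal, unrelated | yes | yes (death information) | yes | yes | first and last |
| Non-fatal, unrelated to both | no | no | no | yes | first and last |
| Non-fatal, 'Unknown' for at least one and related to neither | not stated | not stated | not stated | yes | first; no other block names it |

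**Step 1: which blocks.** The third row feeds only the first and last blocks, so 2 of 6 are affected. The last block would not be empty. It would still hold fatal unrelated SAEs, and section 14 also brings in SAEs during the procedure whatever their relatedness.

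**Step 2: the two readings of the any-SAE sentences.**
- *Narrow:* they refer back to the SAEs just listed, in line with the required SAEs of 14.3. The protocol's notification text is then consistent, and the two blocks are incomplete for what their labels say.
- *Broad:* they cover every SAE. The sponsor is then notified, but 14.3 still restricts eCRF entry, and no section says that the additional SAEs reach the analysis data. Capture could be anything from none to complete.

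**Step 3: direction and size.** Let k be the number of missed events, m the number of subjects with a missed event and no counted SAE in the block, and N the number enrolled. The event count is low by k, and the subject percentage by 100 × m / N. If a subject with a missed event already has a counted SAE in the block, that subject adds nothing to m and the percentage does not move. With the planned N = 200, each subject in m lowers the percentage by 100 × 1 / 200 = 0.5 points. Neither k nor m can be obtained from the documents.

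**Step 4: 'Unknown' relatedness.** The fourth row has no stated collection rule. If such SAEs are collected and counted as related, the related blocks change, and so does the related-SAE secondary endpoint (SAP 5.2.2, item 4). If they are counted as unrelated, the last block changes. The plan does not say which applies.

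**The case against.** The best defence is that this is a matter of labels. The SAP describes itself as coordinated with the protocol, so all SAEs can be read as all SAEs collected under it. SAP section 8 calls its tables samples that may change, and these are additional, descriptive analyses with no hypothesis attached. The eCRF is not in the documents. If every SAE notified to the sponsor is entered, the labels are correct as they stand. 'Unknown' is also a narrow category, because 14.2 already counts a possible link as related.

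Much of this stands, and it limits the consequence. It does not remove the point: no SAP definition or Table 12 footnote restricts the label to collected SAEs, and full capture is possible but not stated anywhere.

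A reader might infer more than the documents support:
- *That the all-SAE rate is certainly too low.* Complete capture under the broad reading is not excluded.
- *That sites will differ in what they enter.* This is plausible under conflicting text but is not shown.
- *That a shortfall can be calculated from the TREVO study's 21.7% (13/60) with SAEs.* That study had its own pre-defined safety events, and no section gives a rate of non-fatal unrelated SAEs to add to it.
- *That the secondary safety endpoints fail.* SAEs judged related and Day 90 mortality are within collection scope. Only the handling of 'Unknown' touches the related-SAE endpoint.

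**Conclusion.** The point holds as a mismatch between table labels and collection scope. As written, the plan would yield an all-SAE percentage and an unrelated-SAE percentage that the protocol's data items do not support. Under the narrow reading, the collection rules leave non-fatal unrelated SAEs after the procedure out of both blocks; under the broad reading, completeness is uncertain. Any error runs towards counts that are too low and percentages that are too low or unchanged, by an amount the documents do not reveal. The conclusion assumes that the eCRF follows 14.3. It is worth correcting before the tables are produced, but it does not touch the primary endpoint or Day 90 mortality. The gap for 'Unknown' relatedness is a smaller, linked defect that could also move the related-SAE figures.

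Section 14.3 also fails to name unrelated non-fatal AEs during the procedure, although section 14 lists them. That bears mainly on Table 13, is a separate matter, and adds no weight here.

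**What to change.** Reconcile protocol 8.4 to 8.6, 14, 14.3 and Appendix D to one SAE collection rule. State in it how SAEs of 'Unknown' relatedness are collected and in which Table 12 block they are counted. Then:

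- **If the section 14 scope stands:** retitle the SAP 5.3 item and Table 12 'SAEs reportable under protocol section 14 through Day 90', and relabel the first block the same way. Relabel the last block 'Not device or procedure related: fatal, or occurring during the procedure'. Add a footnote that other non-fatal SAEs after the procedure not judged related (including 'Unknown', unless the reconciled rule collects them) were not required to be collected and may be incomplete.
- **If the any-SAE wording governs:** align section 14, 14.3, the visit lists, Appendix D and the eCRF to it, and keep the Table 12 labels. If the rule starts part-way through enrolment, footnote which subjects were followed under the previous protocol text.

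**Cost.** In the first case, wording in table shells that the SAP already calls changeable, and the loss of an all-SAE rate. In the second, eCRF changes and more data entry at up to 15 sites. Either way, aligning the protocol text may need an amendment and submission to the ethics committees.

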### 5.4. Descriptive Analyses

#### 5.4.1. Demographics and Baseline Characteristics

Subjects' demographic characteristics will be summarized using descriptive statistic methods.

Continuous variables will be summarized by mean $\pm$ SD, median, minimum and maximum.

Categorical variables will be summarized by percentages and frequencies.

#### 5.4.2. Medical History

Subjects' medical history will be summarized by percentages and frequencies.

#### 5.4.3. Modified Rankin Scale (mRS)

mRS will be summarized by frequencies and percentages and by visits. The difference of mRS from Day 90 to baseline, defined as mRS at Day 90 – mRS at baseline, will be categorized by decreased or no change (mRS from Day 90 - mRS from baseline $\leq$ 0) or increased and will be analyzed by frequencies and percentages.

#### 5.4.4. NIHSS

NIHSS will be summarized by mean  $\pm$  SD, median, minimum and maximum and by visits.

#### 5.4.5. Procedural Characteristics

The continuous variables will be summarized by mean  $\pm$  SD, median, minimum and maximum. The categorical variables will be summarized by frequencies and percentages.

#### 5.4.6. Device Malfunction

All the device malfunction will be summarized by number of device malfunctions, number of device with device malfunction, percentage of device with device malfunction, number of subjects with device malfunctions and percentages of subjects with device malfunctions.

STRYKER CONFIDENTIAL - THIS DOCUMENT CONTAINS CONFIDENTIAL AND PROPRIETARY INFORMATION THAT IS THE PROPERTY OF STRYKER CORPORATION. NEITHER THIS DOCUMENT NOR THE INFORMATION HEREIN MAY BE REPRODUCED, USED, OR DISCLOSED TO ANY THIRD PARTY WITHOUT THE PRIOR WRITTEN CONSENT OF STRYKER CORPORATION

## Stryker Neurovascular

**Document Title:** Trevo® Retriever Registry (China) Statistical Analysis Plan

**Document Number:** CDM10001420

**Ver AA**

### 5.4.7. Time Intervals

Time intervals will include but not limited to time from stroke symptom onset to admission to hospital/emergency department, intravenous tissue plasminogen (IV tPA), angio suite, arterial puncture, first Trevo® deployed, last Trevo® deployed and the end of the procedure. Time of clot integration, is calculated from the Trevo® deployed to the Trevo® starting to pulled.

### 5.5. Subgroup Analyses

Sub-group analyses (such as ICAD, IV Lytic use) for the Registry will be performed as needed.

### 5.6. Ad hoc Analyses

Ad hoc analyses will be generated as needed.

## 6. Analyses Schedule

### 6.1. Interim Analyses

Interim analysis may be performed as needed.

### 6.2. Final Report

Final report will be generated when all the 200 enrolled subjects complete their Day 90 visit or terminated before their Day 90.

## 7. Analysis Software

All statistical analyses will be generated using SAS® 9.4 or higher.

STRYKER CONFIDENTIAL - THIS DOCUMENT CONTAINS CONFIDENTIAL AND PROPRIETARY INFORMATION THAT IS THE PROPERTY OF STRYKER CORPORATION. NEITHER THIS DOCUMENT NOR THE INFORMATION HEREIN MAY BE REPRODUCED, USED, OR DISCLOSED TO ANY THIRD PARTY WITHOUT THE PRIOR WRITTEN CONSENT OF STRYKER CORPORATION

# Stryker Neurovascular

**Document Title:** Trevo® Retriever Registry (China) Statistical Analysis Plan

**Document Number:** CDM10001420

**Ver AA**

## 8. Analysis Table Template

The following tables are provided as samples and are subject to change as needed.

**Table 1 Subjects Disposition**

	Number of Subjects Enrolled (N=xxx*)	Subjects Eligible at 24 Hours (-6/+24) post procedure (N=xxx*)	Subjects Eligible at Discharge/Day 5-7 (whichever comes first) (N=xxx*)	Subjects Eligible at Day 30 (N=xxx*)	Subjects Eligible at Day 90 (N=xxx*)
Visit Completed	xx (xx.x%)	xx (xx.x%)	xx (xx.x%)	xx (xx.x%)	xx (xx.x%)
Visit Not Completed	xx (xx.x%)	xx (xx.x%)	xx (xx.x%)	xx (xx.x%)	xx (xx.x%)
Reason for not completing the visit					
Missed Visit	NA	xx (xx.x%)	xx (xx.x%)	xx (xx.x%)	xx (xx.x%)
Early Termination	NA	xx (xx.x%)	xx (xx.x%)	xx (xx.x%)	xx (xx.x%)
List Reason for Early Termination **	NA	xx (xx.x%)	xx (xx.x%)	xx (xx.x%)	xx (xx.x%)
*: N = Number of subjects expected at this visit					
**: The percentage is calculated based on the number of early terminations.					

STRYKER CONFIDENTIAL - THIS DOCUMENT CONTAINS CONFIDENTIAL AND PROPRIETARY INFORMATION THAT IS THE PROPERTY OF STRYKER CORPORATION. NEITHER THIS DOCUMENT NOR THE INFORMATION HEREIN MAY BE REPRODUCED, USED, OR DISCLOSED TO ANY THIRD PARTY WITHOUT THE PRIOR WRITTEN CONSENT OF STRYKER CORPORATION

# Stryker Neurovascular

**Document Title:** Trevo® Retriever Registry (China) Statistical Analysis Plan

**Document Number:** CDM10001420

**Ver AA**

**Table 3: Baseline Demographics and Clinical Characteristics**

	Number of Subjects (N=xxx)
Age	
Mean ± SD (N)	xx.x ± xx.x (xxx)
Median (Q1, Q3)	xx.x (xx.x, xx.x)
Range (min, max)	xx.x (xx.x, xx.x)
Gender	
Male	xx.x% (xx/xxx)
Female	xx.x% (xx/xxx)
Body Mass Index	
Mean ± SD (N)	xx.x ± xx.x (xxx)
Median (Q1, Q3)	xx.x (xx.x, xx.x)
Range (min, max)	xx.x (xx.x, xx.x)
Medical History	
Hypertension (HTN)	xx.x% (xx/xxx)
Heart Failure (CHF)	xx.x% (xx/xxx)
Coronary Artery Disease (CAD)	xx.x% (xx/xxx)
Extracranial Carotid Artery Disease	xx.x% (xx/xxx)
Left	xx.x% (xx/xxx)
Right	xx.x% (xx/xxx)
Bilateral	xx.x% (xx/xxx)
Atrial Fibrillation (A-fib)	xx.x% (xx/xxx)
Peripheral Vascular Disease (PWD)	xx.x% (xx/xxx)
Diabetes Mellitus	xx.x% (xx/xxx)
Other	xx.x% (xx/xxx)
Dyslipidemia	xx.x% (xx/xxx)
Current Smoker (within last year)	xx.x% (xx/xxx)
Past Smoker (>1 year ago)	xx.x% (xx/xxx)
Previous Transient Ischemic Attack (TIA)	xx.x% (xx/xxx)
Previous Ischemic Stroke	xx.x% (xx/xxx)
Previous Ischemic Stroke in the same territory	xx.x% (xx/xxx)
Previous Intra-cerebral Hemorrhage	xx.x% (xx/xxx)
Previous History of known ICAD (intracranial atherosclerotic disease)	xx.x% (xx/xxx)
History of Alcohol Abuse	xx.x% (xx/xxx)
Other	xx.x% (xx/xxx)

STRYKER CONFIDENTIAL - THIS DOCUMENT CONTAINS CONFIDENTIAL AND PROPRIETARY INFORMATION THAT IS THE PROPERTY OF STRYKER CORPORATION. NEITHER THIS DOCUMENT NOR THE INFORMATION HEREIN MAY BE REPRODUCED, USED, OR DISCLOSED TO ANY THIRD PARTY WITHOUT THE PRIOR WRITTEN CONSENT OF STRYKER CORPORATION

## Stryker Neurovascular

**Document Title:** Trevo® Retriever Registry (China) Statistical Analysis Plan

**Document Number:** CDM10001420

**Ver AA**

**Table 4: Baseline Lab**

	Number of Subjects (N=xxx)
Platelets (10^9/L)	
Mean ± SD (N)	xx.x ± xx.x (xxx)
Median (Q1, Q3)	xx.x (xx.x, xx.x)
Range (min, max)	xx.x (xx.x, xx.x)
PT (sec)	
Mean ± SD (N)	xx.x ± xx.x (xxx)
Median (Q1, Q3)	xx.x (xx.x, xx.x)
Range (min, max)	xx.x (xx.x, xx.x)
PTT (sec)	
Mean ± SD (N)	xx.x ± xx.x (xxx)
Median (Q1, Q3)	xx.x (xx.x, xx.x)
Range (min, max)	xx.x (xx.x, xx.x)
INR (RATIO)	
Mean ± SD (N)	xx.x ± xx.x (xxx)
Median (Q1, Q3)	xx.x (xx.x, xx.x)
Range (min, max)	xx.x (xx.x, xx.x)
Blood Glucose (mmol/L)	
Mean ± SD (N)	xx.x ± xx.x (xxx)
Median (Q1, Q3)	xx.x (xx.x, xx.x)
Range (min, max)	xx.x (xx.x, xx.x)

STRYKER CONFIDENTIAL - THIS DOCUMENT CONTAINS CONFIDENTIAL AND PROPRIETARY INFORMATION THAT IS THE PROPERTY OF STRYKER CORPORATION. NEITHER THIS DOCUMENT NOR THE INFORMATION HEREIN MAY BE REPRODUCED, USED, OR DISCLOSED TO ANY THIRD PARTY WITHOUT THE PRIOR WRITTEN CONSENT OF STRYKER CORPORATION

## Stryker Neurovascular

**Document Title:** Trevo® Retriever Registry (China) Statistical Analysis Plan

**Document Number:** CDM10001420

**Ver AA**

**Table 5: Procedural Characteristics**

	Number of Subjects (N=xxx)
IA Medication Administered at Site of Thrombus	xx.x% (xx/xxx)
Drug Type	
Lytic Used	xx.x% (xx/xxx*)
Anti-vasospasm	xx.x% (xx/xxx*)
Other	xx.x% (xx/xxx*)
Clot Location	
CA - cervical	xx.x% (xx/xxx)
CA - petrous	xx.x% (xx/xxx)
ICA - cavernous	xx.x% (xx/xxx)
ICA - supraclinoid	xx.x% (xx/xxx)
ICAT bif	xx.x% (xx/xxx)
A1	xx.x% (xx/xxx)
A2	xx.x% (xx/xxx)
MCA-M1	xx.x% (xx/xxx)
MCA-M2	xx.x% (xx/xxx)
MCA-M3	xx.x% (xx/xxx)
Vert	xx.x% (xx/xxx)
P1	xx.x% (xx/xxx)
P2	xx.x% (xx/xxx)
Target Vessel - Laterality	
Right	xx.x% (xx/xxx)
Left	xx.x% (xx/xxx)
Target Vessel Pass Basilar	
Proximal	xx.x% (xx/xxx)
Mid	xx.x% (xx/xxx)
Distal tip	xx.x% (xx/xxx)
Baseline Imaging	
CTP/CTA	xx.x% (xx/xxx)
MRI/MRA	xx.x% (xx/xxx)
Non-Contrast CT Only	xx.x% (xx/xxx)
Embolization to New Territory Observed	xx.x% (xx/xxx)
Distal Embolization Observed	xx.x% (xx/xxx)
Number Passes of Trevo® Retriever(s)	
Mean $\pm$ SD (N)	xx.x $\pm$ xx.x (xxx)

STRYKER CONFIDENTIAL - THIS DOCUMENT CONTAINS CONFIDENTIAL AND PROPRIETARY INFORMATION THAT IS THE PROPERTY OF STRYKER CORPORATION. NEITHER THIS DOCUMENT NOR THE INFORMATION HEREIN MAY BE REPRODUCED, USED, OR DISCLOSED TO ANY THIRD PARTY WITHOUT THE PRIOR WRITTEN CONSENT OF STRYKER CORPORATION

## Stryker Neurovascular

**Document Title:** Trevo® Retriever Registry (China) Statistical Analysis Plan

**Document Number:** CDM10001420

**Ver AA**

Median (Q1-Q3)	xx.x (xx.x, xx.x)
Range (Min-Max)	xx.x (xx.x, xx.x)
1 pass	xx.x% (xx/xxx)
2 passes	xx.x% (xx/xxx)
>=3 passes	xx.x% (xx/xxx)
Number Passes of All Thrombectomy Device(s)	
Mean $\pm$ SD	xx.x $\pm$ xx.x (xxx)
Median (Q1-Q3)	xx.x (xx.x, xx.x)
Range (Min-Max)	xx.x (xx.x, xx.x)

\*: Denominator is the number of subjects who used IA medicine

STRYKER CONFIDENTIAL - THIS DOCUMENT CONTAINS CONFIDENTIAL AND PROPRIETARY INFORMATION THAT IS THE PROPERTY OF STRYKER CORPORATION. NEITHER THIS DOCUMENT NOR THE INFORMATION HEREIN MAY BE REPRODUCED, USED, OR DISCLOSED TO ANY THIRD PARTY WITHOUT THE PRIOR WRITTEN CONSENT OF STRYKER CORPORATION

# Stryker Neurovascular

**Document Title:** Trevo® Retriever Registry (China) Statistical Analysis Plan

**Document Number:** CDM10001420

**Ver AA**

**Table 6: Time Intervals**

Time Intervals*	Number of Subjects (N=xx)
Stroke symptom onset to first hospital	
Mean ± SD (N)	xx.x ± xx.x (xxx)
Median (Q1, Q3)	xx.x (xx.x, xx.x)
Range (min, max)	xx.x (xx.x, xx.x)
Stroke symptom onset to second hospital	
Mean ± SD (N)	xx.x ± xx.x (xxx)
Median (Q1, Q3)	xx.x (xx.x, xx.x)
Range (min, max)	xx.x (xx.x, xx.x)
Stroke symptom onset to primary hospital	
Mean ± SD (N)	xx.x ± xx.x (xxx)
Median (Q1, Q3)	xx.x (xx.x, xx.x)
Range (min, max)	xx.x (xx.x, xx.x)
Stroke symptom onset to IV Lytic	
Mean ± SD (N)	xx.x ± xx.x (xxx)
Median (Q1, Q3)	xx.x (xx.x, xx.x)
Range (min, max)	xx.x (xx.x, xx.x)
Stroke symptom onset to angiography suite	
Mean ± SD (N)	xx.x ± xx.x (xxx)
Median (Q1, Q3)	xx.x (xx.x, xx.x)
Range (min, max)	xx.x (xx.x, xx.x)
Stroke symptom onset to arterial puncture	
Mean ± SD (N)	xx.x ± xx.x (xxx)
Median (Q1, Q3)	xx.x (xx.x, xx.x)
Range (min, max)	xx.x (xx.x, xx.x)
Stroke symptom onset to first Trevo® deployed	
Mean ± SD (N)	xx.x ± xx.x (xxx)
Median (Q1, Q3)	xx.x (xx.x, xx.x)
Range (min, max)	xx.x (xx.x, xx.x)
Stroke symptom onset to last Trevo® deployed	
Mean ± SD (N)	xx.x ± xx.x (xxx)
Median (Q1, Q3)	xx.x (xx.x, xx.x)
Range (min, max)	xx.x (xx.x, xx.x)
Stroke symptom onset to the end of procedure	
Mean ± SD (N)	xx.x ± xx.x (xxx)
Median (Q1, Q3)	xx.x (xx.x, xx.x)

STRYKER CONFIDENTIAL - THIS DOCUMENT CONTAINS CONFIDENTIAL AND PROPRIETARY INFORMATION THAT IS THE PROPERTY OF STRYKER CORPORATION. NEITHER THIS DOCUMENT NOR THE INFORMATION HEREIN MAY BE REPRODUCED, USED, OR DISCLOSED TO ANY THIRD PARTY WITHOUT THE PRIOR WRITTEN CONSENT OF STRYKER CORPORATION

